3.2.1.5 Multicenter Studies

Approximately 135 patients are planned for the parent study may be eligible to enroll into this OLE study. Adjustment for investigative site in multivariable analyses is not planned.

3.2.2 Patient Populations Analyzed

The following analysis populations are defined for this present OLE study:

- Screened patients will be defined as patients who signed an informed consent form.
- Enrolled patients will be defined as patients who signed an informed consent form and were not screen failures.
- The FAS will include all enrolled patients who received at least 1 injection of ISIS420915 in the
 OLE study and who have at least one post-baseline efficacy assessment for the mNIS+7 score or
 Norfolk QOL-DN questionnaire total score collected after CS3 Study Day 1 in this OLE study. This
 will be the primary population for analysis of efficacy and PD outcomes.
- The Safety Set (SS) will include all enrolled patients who received at least 1 injection of ISIS
 420915 in the OLE study. This population will beused for analyses of all safety measures
 collected in this OLE study. Results will be summarized under the treatment which the patients
 received in the parent study.
- The Longitudinal Safety Set (LSS): will include all patients who received at least 1 injection of ISIS 420915 in the parent study. This population will beused for the longitudinal safety analysis for either the parent study or this OLE study. Results will besummarized under the treatment which the patients received in the parent study. Note that this population will include patients who receive ISIS 420915 in the parent study but did not enter this OLE. It does not include patients who took placebo in CS2.
- The PPS will include the subset of the Full Analysis Set that have received at least 70% of the prescribed doses of ISIS 420915 in this OLE study and that have no significant protocol deviations in the OLE study that would be expected to affect efficacy assessments. Prescribed doses of ISIS420915 mentioned above is defined as the total assigned dose in mg from the Week 1 to the last dose within this study up to week 156 (first three years), i.e. 300mg*156 doses= 46800mg. Patients in FAS of this OLE study but excluded from PPS in the parent study will be excluded from the PPS in this OLE study as well. This will be a secondary population for

efficacy and PD analyses. The detailed criteria and definitions for major protocol violations will be specified. Results will be summarized under the treatment which the patients received in the parent study.

- The PK Set will include all enrolled patients who received at least one dose of ISIS 420915 in the OLE study and have at least one evaluable PK sample collected and analyzed with reportable result in the OLE study. This population will be used for PK analyses. Results will be summarized under the treatment which the patients received in the parent study.
- The ECHO subgroup in the parent study will include the subset of the Randomized Set that
 qualified and consented for the ECHO sub study in the parent study. The ECHO subgroup in this
 OLE study will include the ECHO subgroup patients who are enrolled in this OLE study. Results
 will be summarized under the treatment to which patients were randomized in the parent
 study.
- The CM-ECHO set in the parent study will include the subset of the Randomized Set that meet at least one of the following criteria, 1) diagnosis of TTR cardiomyopathy at study entry, or 2) eligible to participate in the ECHO Subgroup in the parent study (whether consented or not). The CM-ECHO set in this OLE study will include the CM-ECHO set patients from the parent study who are enrolled in this OLE study. Results will be summarized under the treatment to which patients were randomized in the parent study.
- The CS3 ECHO Set will include the subset of the CS3 Enrolled Set who were not in the CM-ECHO
 Set in the parent study, and were randomized to placebo in the parent study and had an OLE
 study baseline value of either interventricular septum thickness ≥ 1.3 cm or posterior wall
 thickness ≥ 1.3 cm.

All efficacy and PD endpoints (except ECHO parameters) will be assessed on the FAS and PPS. All safety assessments for this OLE study will be performed on the Safety Set. The longitudinal safety analysis will be performed on the Longitudinal Safety Set. PK endpoints will be assessed in the PK Set as applicable.

3.2.3 Patient Characteristics

Patients disposition, including reasons for permanent discontinuation from ISIS 420915 or withdrawal from follow-up, and number of patients in each analysis population (FAS, PPS, SS, LSS, PKS, ECHO Subgroup, CM-ECHO Set), will be summarized by treatment group of the parent study and overall for all enrolled patients.

Patient's allocation by investigative site will be tabulated by parent study treatment group and overall for the all enrolled patients.

Protocol deviations in OLE study will be listed and summarized by deviation category.

The following patients' demographic characteristics will be summarized by treatment group of the parent study and overall for the SS, FAS, PPS, PKS, CM-ECHO Set and ECHO subgroups:

• Sex, race, ethnicity, TTR genotype

- Age at the parent study screening and age at the OLE study screening
- Duration derived from the informed consent form signed date in the OLE study, including duration of disease from FAP diagnosis (months) and duration from onset of FAP symptoms (months)

Number and percent of enrolled patients within each of the 3 randomization strata from the parent study (previous treatment with Vyndaqel® or Diflunisal; disease stage; V30M TTR mutation) will be summarized by treatment group of the parent study and overall for the SS, FAS, PPS, PKS, CM-ECHO Set and ECHO subgroups.

The following will be provided for both **parent study baselines** and **OLE study baselines** defined in section 3.2.1.1 and for the SS, FAS, PPS, PKS, CM-ECHO Set and ECHO subgroups:

Baseline severity of illness, including the NIS score, NIS+7, mNIS+7, PND score, mBMI, BMI, weight, height, and NT-proBNP will be summarized by parent study treatment group and overall. Measures of quality of life and level of functioning, including the baseline Norfolk QOL-DN total score and predose SF-36 will also be included. Disease history collected in the parent study will be summarized for analysis sets defined above: Information on familial amyloid cardiomyopathy (FAC) will be summarized, including FAC diagnosis (Y/N) at parent study screening, duration of disease from FAC diagnosis (months), duration from onset of FAC symptoms (months), and clinical or laboratory criteria used to document the diagnosis of TTR cardiomyopathy.

Missing/partial dates (month and year) for the duration of disease from diagnosis for FAP/FAC and duration from onset of symptoms for FAP/FAC will be imputed as follows: since CRF only collects year and month for FAP and FAC Diagnosis and onset of symptoms, for calculating the duration, a day of 15th will be used if only day is missing. JUL01 will be used if both day and month are missing. If the imputed date is after the date of informed consented at CS2, use the informed consented at CS2 as the imputed date. Calculate as following

- (a) Duration (month) = number of month (date of informed consented at CS3- date of FAP or FAC diagnosis + 1)
- (b) Duration (month) = number of month (date of informed consented at CS3- date of onset of FAP or FAC symptoms + 1)

Exposure to Study Drug in OLE study will be summarized by treatment group of the parent study for the SS by durations of drug exposure in OLE study (days), total number of dose received, and total dose administered (in milligrams). Across all visits, number of subjects with dose pauses and reasons for dose pause will be tabulated. A listing presenting for each subject the number of dose reductions (frequency of administered dose < protocol defined dose, i.e. 300 mg) and missed doses (injection not givens) will be provided. Doses that were not given because the patient discontinued will not be summarized.

Overall drug exposure from the start of the parent study to the end of the OLE study will be summarized for patients who took ISIS 420915 in the parent study, i.e. LSS.

Medical history and baseline physical examination findings collected in the OLE study will be listed depending on the data availability.

Medications will be coded using WHO Drug Dictionary. The final version used will be designated in the clinical study report. Concomitant medications used will be summarized by treatment group for the SS and the CM-ECHO Set.

All medications including concomitant medications will also be listed in a by patient listing. In the listing, medications which are started before the **CS3 Study Day 1** will be marked.

Patients with any anti-platelet or anti-coagulant medication taken at any time during this study will be presented in a listing.

A concomitant medication is defined as any medication taken whilst investigational product is being taken in this study.

If a partial date is recorded in the case report form, the following convention will be used to assign the medication:

- if the partial date is a start date, a '01' will be used for the day and 'Jan' will be used for the month
- if the partial date is a stop date, a '28/29/30/31' will be used for the day (dependent on the month and year) and 'Dec' will be used for the month.

The recorded partial date will be displayed in listings.

The definitions for on-treatment and on-study concomitant medication defined relative to use of the investigational product are shown schematically in the diagram below.

			CM	
Scenario	On-treatment	Post-treatment	On-treatment	On-study
1	x x		Υ	Y
2	x x		Y	Υ
3		x x	N	Y
4	?x		Y	Y
5	?x		Y	Υ
6	x?		Y	Y
7		x?	N	Y

CM -concomitant medication

x = start/stop date/time

? = missing date/time

3.3 Safety Analyses

All safety endpoints will be summarized for the OLE study SS. In patient listings, **ISIS 420915 baseline** values and information collected in the OLE study will be displayed. In addition, longitudinal safety analysis of selected safety endpoints for LSS will be performed for patients on ISIS 420915 in the parent study.

Safety endpoints include the following:

- Adverse events
- Vital signs and weight
- Physical examination
- Clinical laboratory tests
- ECG
- Ophthalmology and ERG examinations

3.3.1 Imputation of Missing/Partial Dates

The following imputation rules will be applied to impute AE start dates under conservative principles. If the month, year, and day are missing, the adverse event start date will be imputed as the treatment start date. If month and day are missing and year is available and is the same year as in treatment start date, the month and day from the treatment start date will be used to impute the missing month and day for the adverse event start date. Otherwise, missing month and day will be imputed as January 01. If day is missing and month and year is available and the month and year are the same month and year in treatment start date, the day from the treatment start date will be used to impute missing day for the adverse event start date. Otherwise, missing day will be imputed as 01.

Note: Treatment start date mentioned above is CS3 Study Day 1 in general. In addition, special considerations should be given to AEs which started in the parent study but continued at the time the patient enrolled in the OLE study. If the AE was originally recorded in the CS2 database, the treatment start date mentioned above is from CS2 but not CS3 Study Day 1.

3.3.2 Adverse Events (AEs)

Adverse events will be coded using Medical Dictionary for Regulatory Activities (MedDRA). The final version used will be designated in the clinical study report. For each AE, the severity level of the event (mild, moderate, or severe) will be determined by physician opinion.

TEAEs are defined as adverse events that first occurred or worsened after the first dose of Study Drug (ISIS 420915 or Placebo). This is the general definition of TEAEs. A detailed definition of TEAEs for safety analysis of the OLE study or for the longitudinal safety analysis will be discussed in section 3.3.2.6 or in section 3.3.2.7, respectively.

In this section, whenever first dose of ISIS 420915 is used, it refers to **CS3 Study Day 1** for OLE study analysis and **Day 1 of ISIS 420915** for longitudinal safety analysis.

An AE with a completely missing start date will be assumed to be treatment emergent.

If the maximum severity of the adverse event is greater than the baseline severity, i.e. severity prior to the first dose of ISIS 420915, or if the onset date/time is the same as or after the date/time of the first dose of ISIS 420915, then the event is considered to be treatment emergent.

In the situation where change in severity (but no change in seriousness) occurs for an adverse event, study sites are instructed to enter an end date and start a new record for the adverse event. In the new record, the changed severity is to be recorded and the start date will be set to be the end date of the previous record. Data linking those records are collected in the database. Consider three scenarios:

- The first AE record occurs prior to the first dose of ISIS 420915, the second AE record occurs on
 or after the first dose of ISIS 420915, and the severity increases: Only the second record will be
 counted as treatment-emergent.
- The first AE record occurs prior to the first dose of ISIS 420915, the second AE record occurs on or after the first dose of ISIS 420915, and the severity decreases: Neither record will be counted as treatment-emergent.
- Both records occur on or after the first dose of ISIS 420915: If the AE severity on the second record is worse than the severity on the first record, then count both records as treatmentemergent. But, if the severity improves, then only count the first record as treatmentemergent.

Of note, when counting the total number of treatment-emergent events, events linked through change in severity will still be counted as separate events.

In addition, special considerations should be given to AEs which started in the parent study but continued at the time the patient enrolled in the OLE study. These situations may occur if the outcome of the AE is "Ongoing" or the stop date is missing in the parent study. Records for these AEs will be created in the OLE study database with a different AE index number so that they can be updated with information collected in the OLE study, e.g. stop date and treatment. The following rules describe how these AEs will be handled in the OLE study analysis for SS and the longitudinal safety analysis for LSS:

• For AEs with the same Lower level term (LLT), complete start date and severity recorded in both the parent study and the OLE study: keep the record in the OLE Analysis Data Model (ADaM) dataset, but this record is not considered treatment emergent in CS3. In the longitudinal safety analysis, this record will be counted once (it is considered treatment emergent in CS2 and therefore considered treatment emergent in the longitudinal safety analysis).

Note that an event which started during the gap period between the parent study and the OLE study will not be considered treatment emergent in the CS3 analysis, unless the severity of the event has increased after the first dose in CS3. Such events will be regarded as treatment emergent in the

longitudinal safety analysis (see below) conducted on the LSS. Since subjects randomized to placebo in the parent study are not included in the LSS, if a placebo subject from the parent study experiences such an event, that event will not be summarized in any of the CS2, CS3 or longitudinal safety analyses.

A listing will be provided stating which patients reported each preferred term. Adverse events in the following categories will be summarized separately:

- Adverse events of special interest
- · Other adverse events of interest

Summary tables of the number and percentage of patients with these adverse events will be displayed split by AEcategory and treatment group. TEAEs of special interest and other TEAEs of interest will also be summarized for patients in the CM-ECHO Set.

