9.4.3.5 Outcome of the Adverse Event

If the event is a non-serious AE then the event's outcome is characterized by 1 of the following:

- AE Persists: Patient terminates from the trial and the AE continues
- **Recovered:** Patient recovered completely from the AE
- **Became Serious:** The event became serious (the date that the event became serious should be recorded as the Resolution Date of that AE and the Onset Date of the corresponding SAE)
- Change in Severity (if applicable): AE severity changed

If the event is an SAE then the event's outcome is characterized by 1 of the following:

- Ongoing: SAE continuing
- **Persists (as non-serious AE):** Patient has not fully recovered but the event no longer meets serious criteria and should be captured as an AE in the non-serious AE eCRF (the SAE resolution date should be entered as the date of onset of that AE)
- **Recovered:** Patient recovered completely from the SAE (the date of recovery should be entered as the SAE resolution date)
- Fatal: Patient died (the date of death should be entered as the SAE resolution date)

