Mortality defined in section 3.3.2.5 on SS will be summarized.

A plot of incidence rates and relative risks for common TEAEs, with an incidence of 5% or more, by treatment group assigned in the parent study will be provided.

Summary of non-serious common TEAEs, with an incidence of 5% or more, will be presented by Preferred Term.

Summary tables of the number and percentage of patients with drug related bleeding TEAEs will be presented by bleeding location and Preferred Term.

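### A serious adverse event that began before dosing and later steps down to non-serious becomes a new treatment-emergent event under SAP 3.3.2

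*Combined protocol and SAP*

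**What the plan says.** Protocol 9.4.3.5 lists the possible outcomes of an SAE. If the patient has not fully recovered but the event no longer meets a seriousness criterion, the site makes a new entry on the non-serious AE form, and "the SAE resolution date should be entered as the date of onset of that AE".

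SAP 3.3.2 defines a TEAE in general terms as an event that begins or gets worse after the first dose. Its operating rule has two routes: maximum severity above the pre-dose severity, "or if the onset date/time is the same as or after the date/time of the first dose of ISIS 420915". First dose means CS3 Study Day 1 for the OLE analysis and Day 1 of ISIS 420915 for the longitudinal analysis.

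Three scenarios then cover an event held on more than one record. They are introduced with the words "In the situation where change in severity (but no change in seriousness) occurs for an adverse event". The site closes the old record and opens another, and "the start date will be set to be the end date of the previous record". The scenarios are:

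- Starts before dosing, worsens after: only the second record is treatment-emergent.
- Starts before dosing, improves after: neither record is.
- Both records after dosing: "If the AE severity on the second record is worse than the severity on the first record, then count both records as treatmentemergent". If severity improves, only the first counts.

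The section adds that, in the total of treatment-emergent events, "events linked through change in severity will still be counted as separate events". It gives no rule for a record split by a change in seriousness.

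In SAP 3.3.2.6 the main tables give the percentage of patients by system organ class and preferred term. The section also states: "Summary of non-serious common TEAEs, with an incidence of 5% or more, will be presented by Preferred Term".

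**The concern.** Safety is the primary objective, so the TEAE rules govern the study's main output. The protocol makes sites split a continuing event when its seriousness changes, and the SAP handles splits only when seriousness does not change. The non-serious tail of an SAE therefore falls to the onset-date rule, which sees a fresh onset date and nothing of the earlier history.

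Two results follow. An SAE that began before the first dose and is resolving can appear as a treatment-emergent event in a patient who had none under that term. An SAE that began on drug can appear a second time as a separate treatment-emergent record, with a later start that may fall in a later exposure-duration or dose-number band.

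The situation is foreseeable: protocol 9.4 and SAP 3.3.2 both provide for parent-study events still ongoing at entry to the extension.

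**Working it through.** The documents state no figure on this point, so there is none to reproduce. The check applies the recording and counting rules to single continuing events.

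**Rules applied**

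- First record: counted if its onset is on or after the first dose.
- Later record, seriousness unchanged: counted if it starts on or after the first dose and its severity is higher than on the previous record (the SAP 3.3.2 scenarios, applied pair by pair).
- Later record, seriousness changed: outside the scenarios, so counted if its onset is on or after the first dose (protocol 9.4.3.5 with the SAP 3.3.2 onset-date rule).
- Comparator: 1 if the continuing event began or worsened after the first dose, otherwise 0.

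**Results**

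| One continuing event | Records counted under SAP 3.3.2 | Comparator |
|---|---|---|
| Pre-dose severe SAE, non-serious after dosing (still severe, or mild) | 1 | 0 |
| Pre-dose moderate, mild after dosing, seriousness unchanged | 0 | 0 |
| Pre-dose mild, moderate after dosing, seriousness unchanged | 1 | 1 |
| Post-dose SAE, later non-serious | 2 | 1 |
| Post-dose AE, becomes an SAE, then non-serious | 3 | 1 |
| Post-dose mild, then moderate, then severe | 3 | 1 |
| Post-dose severe, then moderate, then mild | 1 | 1 |

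The first two rows carry the point. Both describe a pre-dose event that does not worsen after dosing. The SAP counts 0 when seriousness is unchanged and 1 when the event also stops being serious.

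**Do other rules in SAP 3.3.2 catch the first row?**

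- The carry-over rule for parent-study events requires the same lower level term, complete start date and severity in both studies. The step-down record has a new start date, so it does not match.
- The rule for events that began between the two studies excludes them unless severity rises. It covers only that interval, and applying it to a step-down record requires knowing which SAE the record continues. The SAP describes linking data for severity splits only.

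**Which analysis is affected?** In the OLE analysis the first row applies to an SAE that began before CS3 Study Day 1. In the longitudinal analysis it applies only to an SAE that began before Day 1 of ISIS 420915. A parent-study SAE that began on drug and stepped down later gives the 2-record row there.

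**The case against.** The strongest reply is that the intent is clear. The general definition, the second scenario and the rule for events between the studies all exclude an event that does not worsen after dosing, so a careful programmer would exclude a step-down as well. Links between SAE and AE records may also exist in the eCRF or the Data Management Plan, which are not available here. The intent is indeed clear, but the operating rule gives the opposite answer, and the SAP neither says which prevails nor names the link needed to follow the intent.

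Rarity stands as an objection. Entry generally requires no significant tolerability issues in the parent study, and patients with a new or worsening condition judged unsuitable are excluded. No hypothesis is tested.

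Four stronger readings are tempting and are not supported:

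- *Event totals only measure how often records were split.* Separate counting of linked severity records is an openly stated convention. It adds to the total only when severity worsens after dosing, because improving records are dropped, and it leaves patient percentages unchanged.
- *Every on-drug SAE that steps down enters the non-serious table.* That table takes only terms with an incidence of 5% or more.
- *That table double-counts patients with SAEs.* A patient may appear in both the serious and the non-serious summaries, but incidence counts the patient once in each.
- *The effect is 2.2 percentage points.* This is 1/45 = 2.2%, but 45 is the planned placebo arm of the parent study, not extension enrolment, and the one patient is assumed.

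**Conclusion.** The point holds for changes in seriousness. Followed literally, SAP 3.3.2 turns the improvement of a pre-dose SAE into a treatment-emergent event, against the SAP's own definition and its second scenario. The effect per case is 0 becoming 1, and it reaches the patient percentage if the patient has no other TEAE under that term. For an SAE that began on drug, 1 event becomes 2 records. The patient percentage for the term does not change, but the non-serious summary and the exposure bands may.

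The conclusion rests on reading protocol 9.4.3.5 together with SAP 3.3.2, since no single sentence states it, and on the absence of any SAE-to-AE link in the documents. The number of cases is probably small and cannot be estimated, because the documents give no AE counts. The separate counting of linked severity records is a matter of labelling.

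**What to change.** In SAP 3.3.2:

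- Extend the linked-record scenarios to changes in seriousness. Match SAE and AE records on term and on SAE end date equal to AE start date, with manual review where a date is partial or the term has changed.
- State that a step-down from serious to non-serious without a rise in severity is not a new treatment-emergent event.
- Take treatment emergence from the first record plus any worsening after dosing. Where only the worsening is treatment-emergent, use its date as the onset for the exposure-duration and dose-number bands in SAP 3.3.2.6 and 3.3.2.7. The first scenario is then unchanged. Giving every chain its first onset would conflict with that scenario and with the bands.
- Say how an AE that becomes serious is handled, since protocol 9.4.3.5 splits that record in the same way.
- Keep the separate counting of linked severity records if wanted, but label the total as a count of records.

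The cost is SAP wording, one derivation in the AE dataset and a short manual review. No new data are collected. In the table above, the first row goes from 1 to 0 and the post-dose SAE that steps down from 2 to 1. The row with a pre-dose mild event that becomes moderate stays at 1.
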